#### COMPLIANCE STATEMENT

This study will be conducted in compliance with Good Clinical Practice (and in accordance with the Declaration of Helsinki) as well as all applicable local regulations.

# SYNOPSIS

Regulatory Classification:	Class II Staple Implantable; Stapler, Surgical 21CFR 878.4750. Cleared 11/24/2014, 510(k) # K141952 CE Mark granted 02/27/2015, Certificate, G7 15 02 57666 049
Indication:	The ECHELON FLEX ™ Powered Vascular Stapler (PVS) with Advanced Placement Tip and its reloads are intended for transection and resection of tissue and vasculature. The instruments have application in multiple open or minimally invasive general, gynecologic, urologic, thoracic, and pediatric surgical procedures. The device will be utilized as described in the instruction for use (IFU).

Objective/Primary Endpoints:	The primary objective of the trial is to demonstrate that the frequency of hemostatic interventions/procedures required intra-operatively or post-operatively related to the transection of the renal artery (RA) and renal vein (RV) during laparoscopic nephrectomies and nephroureterectomies with powered vascular stapler (PVS) is not increased when compared to standard of care (SOC).	
	The primary performance endpoint will be:	
	Incidence of hemostatic interventions/procedures completed for intra-operative bleeding related to the transection of the RA and RV during laparoscopic nephrectomies and nephroureterectomies with the use of standard of care stapler (SOC) or powered vascular stapler (PVS) defined as:	
	
 
Hemostasis intervention: bleeding detected and controlled intra-operatively (additional stapling, over-sewing, clip placement, compression, use of suture, sealant, and/or buttress, and/or use of energy); or bleeding that occurs intra- operatively requiring blood or blood product transfusion or an additional surgical procedure (e.g. conversion to open).
 
	
	No hemostasis intervention is defined as no bleeding at the staple line or bleeding that stops after initial blotting of staple line.	
	The primary safety endpoint will be:	
	Incidence of hemostatic interventions /procedures completed for post-operative bleeding related to the transection of the RA and RV during during laparoscopic nephrectomies and nephroureterectomies with the use of SOC or PVS:	
	
 
Hemostasis intervention: bleeding that occurs post-operatively requiring blood or blood product transfusion or an additional surgical procedure (related to RA and RV transection).
 
	
	No hemostasis intervention is defined as no interventions needed for post-operative bleeding (related to RA and RV transection).	

Study Design:	This prospective, randomized, controlled, multi-center study will collect and compare data from the surgeon's current SOC stapler (for RA/RV transection) and powered vascular stapler.	
Number of Subjects (Planned):	Approximately 250 subjects will be randomized	
Diagnosis/Criteria for Inclusion:	
 
Subjects satisfying the following criteria will be eligible for participation in this study:
 
1. Scheduled for a simple or radical laparoscopic nephrectomy or a laparoscopic nephroureterectomy in accordance with the institution's standard of care (SOC);
 
2. Performance status 0-1 (Eastern Cooperative Oncology Group classification), if applicable;
 
3. ASA score ≤ 3;
 
4. No prior history of partial or wedge nephrectomy (on the kidney in which the procedure will be performed);
 
5. Willing to give consent and comply with study-related evaluation and treatment schedule; and
 
	
	6. At least 18 years of age.	
Diagnosis/Criteria for Exclusion:	
 
Subjects will be excluded from the study for any of the following:
 
1. Prior chemotherapy or radiation (within 30 days prior to the procedure or the duration of the subject's enrollment);
 
2. Pregnancy;
 
3. Physical or psychological condition which would impair study participation; or
 
4. The subject is judged unsuitable for study participation by the Investigator for any other reason.
 
	
Finished Product:	ECHELON FLEX ™ Powered Vascular Stapler with Advanced Placement Tip	

Statistical Methods:	Summary statistics and 95% confidence intervals will be provided for the number and frequency of interventions for the set of SOC and PVS subjects separately. This will be performed based on the total number of firings. An intervention is defined as any firing which is classified as hemostasis intervention. Given that it is expected to have at least 300 firings in each group, the sample size of approximately 250 subjects is considered adequate for descriptive summarization of the number and frequency of surgical interventions. Assuming an approximate background intervention rate of 6%, the given sample size will provide reasonable precision in the estimation of the intervention rate to an expected margin of error for a 95% confidence interval of at most 2.9% for each group. To establish that the intervention rate is not increased compared to SOC, a 95% confidence interval for the difference in proportion of firings requiring interventions for PVS minus SOC will be calculated and powered vascular stapler will be considered to have acceptable performance if the upper bound of the 95% confidence interval does not exceed 3%.
	The number and percentage of subjects requiring hemostasis interventions post-operatively that are classified as related to SOC or PVS for RA/RV transection (e.g. need for blood product transfusion or additional surgical procedure) will be summarized for each group as a primary safety endpoint.
	Additional endpoints will be summarized with descriptive statistics and 95% confidence intervals as appropriate for continuous or categorical measurements
	Safety will be assessed through the incidence of AEs and serious adverse events (SAEs), which will be coded using the Medical Dictionary for Regulatory Activities (MedDRA).

	Visit 1	Visit 2	Visit 3	Visit 4
Study Activity	Screening	Procedure	Post-Op through Discharge	4 week followup d (post procedure)
Informed consent	Х			
Demographic information	X			
Relevant medical/surgical history	X	Х		
Inclusion/Exclusion Criteria	Х	Х		
ASA score		Х		
Randomization (SOC or PVS)		Х		
Collection of procedure data a		Х		
Intra-operative interventions on RA/RV		Х		
Post-operative interventionson on RA/RV			Х	Х
Procedure duration		Х		
Device usage data		Х		
Daily volume and characteristics of drainage (drains)			х	x
Concomitant Procedures/interventions, if applicable			Х	x
Surgeon questionnaires b		Х		
Date of hospital admission		Х		
Overall Operating Room (OR) time		Х		
Adverse Events		Х	Х	X
Anticoagulants c	X			
Concomitant medications associated with adverse events		х	Х	x
Date of drain removal, if applicable			Х	Х
Discharge date			Х	
Subject exited from study				Х

#### SCHEDULE OF EVENTS

a. See section 4.7.3.2 for specific details
b. Surgeon Device Questionnaire (*PVS procedures only*). Surgeon Satisfaction and SURG-TLX (*SOC and PVS procedures*)
c. Anticoagulants taken preoperatively (up to 30 days prior to Visit 2), including the stop date
d. Phone call or office visit

# **ETHICS**

#### Institutional Review Board/Ethics Committee

Participating investigators will ensure that this protocol, Informed Consent Document (ICD), ICD or protocol amendments, and if applicable, any other written information provided to the subjects that assist in the decision to participate are reviewed by an Institutional Review Board (IRB) or Ethics Committee (EC) that complies with governmental requirements. The approving IRB/EC will be responsible for the initial and continuing review and approval of this clinical investigation. Participating investigators will be required to promptly report to the IRB/EC as required by the IRB/EC's policies. Additionally, investigators will be required to refrain from making any changes in the clinical investigation plan without Sponsor and IRB/EC approval of an amended protocol, except where necessary to eliminate apparent immediate hazards to study subjects or others.

#### **Applicable Regulations**

This study will be conducted in compliance with Good Clinical Practice and in accordance with the Declaration of Helsinki, ISO 14155:2011, as well as any other applicable local and country regulatory requirements.

#### Subject Information and Consent

Regulations concerning the protection of subjects require that informed consent be obtained before a subject may participate in any clinical investigation.

An IRB/EC approved informed consent must be sought from each subject and must be appropriately documented in the subject's medical record prior to initiating the study. It is the Investigator's responsibility to obtain written informed consent from the subject. The Investigator may delegate this responsibility if appropriately documented.

The informed consent process involves the following: giving a subject adequate information concerning the study, providing adequate time for the subject to consider all available options, responding to the subject's questions, ensuring that the subject has comprehended this information and finally, obtaining the subject's written consent to participate in this study. All subjects in this study should be completely informed about the purpose, risks, benefits, and other pertinent details of this study. The informed consent process is careful to avoid the perception of any coercion or undue influence on, or inducement of, the subject to participate, and does not waive or appear to waive the subject's legal rights. The ICD is presented in native, non-technical language that is understandable to the subject.

Prior to a subject's participation in this study, an ICD will be signed and dated by the subject and person who conducted the consent discussion. The subject will be provided a copy of the signed ICD. The ICD and any other written materials provided to the subject to assist in the decision to participate must be revised whenever new information becomes available that may be relevant to their willingness to participate or continue participation in this study. Revision to the ICD and other written materials will receive IRB/EC approval before implementation. Each subject will be required to sign any amended ICD (as required by the IRB/EC) and will receive a copy of the signed ICD.

# ADMINISTRATIVE REQUIREMENTS

This study is sponsored by Ethicon Endo-Surgery, Inc. (EES, Cincinnati, OH, USA) and will be conducted in approximately eight surgery centers in the United States and/or European Union under a single protocol approved by each participating site's IRB/EC prior to implementation. The principal investigator at each study site is a surgeon qualified by education, experience, and training to perform the study procedure and to assume responsibility for the conduct of this study.

The Data Management and Biostatistics groups of Ethicon Endo-Surgery, Inc.'s Global Surgery Clinical Development will be responsible for the analysis of data from this protocol. An Electronic Data Capture (EDC) system will be utilized by study site personnel to transfer study data from source records (the first point of clinical data capture) onto common electronic case report forms (eCRFs). This system is a web-based, secure electronic software application (Medidata® Rave, [name]). This system was designed and is developed and maintained by Medidata in a manner that is compliant with national and international Good Clinical Practice (GCP) data protection/data privacy and electronic record/electronic signature (e.g. 21 CFR Part 11) regulatory requirements.

#### **Protocol Modifications**

All protocol amendments must be issued by the Sponsor, signed and dated by the Investigator, and should not be implemented without prior IRB/EC only logistical or administrative aspects of the study (e.g., change in Sponsor personnel, change of telephone number(s)). The Investigator will submit the protocol amendments to the IRB approval, except where necessary to eliminate immediate hazards to the subjects or when the change(s) involves /EC as per their local requirements.

# 1.0 INTRODUCTION AND BACKGROUND

Nephrectomy has many indications, for both simple and radical approaches. A simple nephrectomy is indicated in patients with irreversible kidney damage due to symptomatic chronic infection, obstruction, calculus disease, or severe traumatic injury. Simple nephrectomy is also indicated to treat renovascular hypertension due to noncorrectable renal artery disease or severe unilateral parenchymal damage caused by nephrosclerosis, pyelonephritis, reflux dysplasia, or congenital dysplasia of the kidney.

Surgery (traditional or laparoscopic) is the primary treatment for most renal cancers while laparoscopic donor nephrectomy has remained a safe, less invasive, and effective technique for renal allograft procurement.

The most common reason for a nephroureterectomy (removal of the kidney and ureter) is transitional cell carcinoma. Transitional cell carcinoma is a cancer that occurs within the transitional epithelium of the kidney, ureter, and/or bladder.

The surgical procedures performed under this protocol are simple or radical laparoscopic nephrectomies or nephroureterectomies. The laparoscopic approach typically utilizes several small incisions in the abdominal and/or flank area. Through these incisions, a surgeon uses a camera and specialized surgical instruments to conduct the operation and remove the entire affected kidney (and some of the surrounding tissues if indicated). Laparoscopic nephrectomy is associated with less postoperative pain and a faster return to normal activities than open nephrectomy.

The ECHELON FLEX™ Powered Vascular Stapler with Advanced Placement Tip can transect vessels in restricted narrow spaces near delicate vascular anatomy. With its narrow anvil and curved dissection tip, this stapler enhances visibility and provides precise placement.

#### 2.0 STUDY OBJECTIVES

# 2.1 PRIMARY OBJECTIVE

The primary objective of the study is to demonstrate that the frequency of hemostatic interventions/procedures required intra-operatively or post-operatively related to the transection of the renal artery (RA) and renal vein (RV) during simple, radical laparoscopic nephrectomies or laparoscopic nephroureterectomies with PVS is not increased when compared to standard of care (SOC).

#### 3.0 **INVESTIGATIONAL PLAN**

# 3.1 GENERAL DESIGN

This prospective, randomized, controlled, multi-center study will collect and compare data from the surgeon's current SOC stapler (for RA/RV transection) and PVS. Approximately 250 individuals undergoing simple or radical laparoscopic nephrectomies or laparoscopic nephroureterectomies, and who meet study entry criteria, will be randomized in a 1:1 ratio to either the surgeon's current SOC stapler or PVS. Prospective subjects will be informed about the nature of the research, given the ICD to read, and if the subject understands the consent, will be asked to provide written consent (the ICD).

# 3.2 PRIMARY ENDPOINTS

The primary performance endpoint will be:

Incidence of hemostatic interventions/procedures completed for intra-operative bleeding related to the transection of the RA and RV during laparoscopic nephrectomies and nephroureterectomies with the use of standard of care stapler (SOC) or powered vascular stapler (PVS) defined as:

> Hemostasis intervention: bleeding detected and controlled intra-operatively (additional stapling, over-sewing, clip placement, compression, use of suture, sealant, and/or buttress, and/or use of energy); or bleeding that occurs intra-operatively requiring blood or blood product transfusion or an additional surgical procedure (e.g. conversion to open).

No hemostasis intervention is defined as no bleeding at the staple line or bleeding that stops after initial blotting of staple line.

The primary safety endpoint will be:

Incidence of hemostatic interventions /procedures completed for post-operative bleeding related to the transection of the RA and RV during laparoscopic nephrectomies and nephroureterectomies with the use of SOC or PVS:

> Hemostasis intervention: bleeding that occurs post-operatively requiring blood or blood product transfusion or an additional surgical procedure (related to RA and RV transection).

No hemostasis intervention is defined as no interventions needed for post-operative bleeding (related to RA and RV transection).

# 3.3 ADDITIONAL MEASUREMENTS / DATA COLLECTED

- a. Subject demographics;
- b. All adverse events;
- c. Anticoagulants taken preoperatively (up to 30 days prior to Visit 2) and concomitant medications associated with AEs;
- d. Relevant medical/surgical history (including hypertension, if applicable);
- e. Procedure details;
- f. Number of ports;
- g. Overall operating room and procedure duration;
- h. Intraoperative and postoperative surgical interventions (not associated with transection of the RA/RV), if applicable;
- i. Volume of estimated intra-operative blood loss;
- j. Date(s) of drain removal;
- k. Daily volume and characteristics of drainage;
- I. Transfusion of blood or blood products;
- m. Device usability /articulation questions;
- n. Surgeon assessment of visualization;
- o. Surgeon Questionnaires;
- p. Concomitant procedures/interventions, if applicable; and
- q. Length of stay (LOS) from admission through discharge.

The data collected for this study may be used for future research or enhancement of similar surgical tools.

# 4.0 INVESTIGATIONAL PLAN

# 4.1 OVERALL STUDY DESIGN

This is a prospective, randomized, controlled, multi-center study that is intended to demonstrate that the frequency of hemostatic interventions/procedures required intraoperatively or post-operatively related to the transection of the renal artery (RA) and renal vein (RV) during simple, radical laparoscopic nephrectomies or laparoscopic nephroureterectomies with PVS is not increased when compared to standard of care (SOC).

Eligible subjects will be randomized pre procedure in a 1:1 ratio to either the surgeon's current SOC stapler or PVS. Subjects will be followed post-operatively through discharge and at 4 weeks post surgery (final visit can be conducted either by phone or office visit).

If the study surgeons have not completed previous ECHELON FLEX™ Powered Vascular Stapler with Advanced Placement Tip training, each surgeon must complete two procedures with ECHELON FLEX™ Powered Vascular Stapler with Advanced Placement Tip prior to their first randomized subject. These subjects will be considered part of a learning curve and will be analyzed separately from the randomized subjects.

# 4.2 RANDOMIZATION

In this non blinded study, randomization will be used to avoid bias in the assignment of the stapling device to be utilized for RA/RV transection for each subject, to increase the likelihood that attributes of the subject are evenly balanced between groups, and to enhance the validity of statistical comparisons between groups.

The Sponsor will assign the stapling device randomly to each subject on a 1:1 basis to either the surgeon's current SOC or PVS.

In the event that a potential subject fails inclusion/exclusion criteria prior to randomization, this subject will be considered a screen failure.

# 4.2.1 Inclusion Criteria

Subjects satisfying the following criteria will be eligible for participation in this study:

- 1. Scheduled for a simple or radical laparoscopic nephrectomy or a laparoscopic nephroureterectomy in accordance with the institution's standard of care (SOC);
- 2. Performance status 0-1 (Eastern Cooperative Oncology Group classification), if applicable;
- 3. ASA score < 3;
- 4. No prior history of partial or wedge nephrectomy (on the kidney in which the procedure will be performed);
- 5. Willing to give consent and comply with study-related evaluation and treatment schedule; and
- 6. At least 18 years of age.

# 4.2.2 Exclusion Criteria

Subjects will be excluded from the study for any of the following:

- 1. Prior chemotherapy or radiation (within 30 days prior to the procedure or the duration of the subject's enrollment);
- 2. Pregnancy;
- 3. Physical or psychological condition which would impair study participation; or
- 4. The subject is judged unsuitable for study participation by the Investigator for any other reason

All subjects signing consent who do not meet the inclusion/exclusion criteria and therefore do not proceed to Visit 2/Procedure, and are not randomized, will be recorded as screen failures. The relevant electronic Case Report Form (eCRF) pages will be completed for all screen failure subjects and the data will therefore be included in the study database.

# 4.3 PRIOR AND CONCOMITANT THERAPY

Study subjects may continue with their current medical care while in the study, including medications.

# 4.3.1 Concomitant Medications

Anticoagulants taken preoperatively (up to 30 days prior to Visit 2) and medications prescribed due to an adverse event will be collected for this study. No other concomitant medications will be collected.

# 4.4 REMOVAL OF SUBJECTS FROM STUDY

A subject has the right to withdraw from the study at any time for any reason without prejudice to his/her future medical care by the physician or the institution. Should a subject (or subject's legally authorized guardian/representative) decide to withdraw; all efforts will be made to collect and report the final visit observations as thoroughly and timely as possible.

Subjects who withdraw from the study prior to randomization will be considered screen failures and will be replaced. Subjects who withdraw from the study post-randomization, will not be replaced. Subject participation may be terminated prior to completing the study for any of the reasons listed below. When a subject's participation is terminated prior to completing the study, the reason for withdrawal is to be documented on the Study Completion eCRF as well as in the source documentation:

#### Withdrawal of Consent:

The subject withdraws consent for participation in the study. Any method of contact with the subject in which they state they no longer want to participate in the study specific activities constitutes withdrawal of consent. When possible the reason for withdrawal of consent will be documented.

#### Surgical:

The Investigator must withdraw a subject intraoperative for the following reasons:

- A simple or radical laparoscopic nephrectomy or laparoscopic nephroureterectomy not completed;
- Conversion to an open procedure, unless directly related to transection of the RA/RV (subject will be followed for safety up to 30 days postop); or
- Use of robotic assistance during surgery.

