# 7.3 ANALYSIS SETS

•

There will be three analysis sets defined:

The Full Analysis Set (FAS) will consist of all randomized subjects who had the

procedure performed and provide data on number of surgical interventions;

- The Per Protocol (PP) Analysis Set will consist of all subjects in the FAS who had no major protocol violations;
- The Safety Set consists of all randomized subjects on whom the procedure is started.

The primary performance endpoint analysis will be performed on the Full Analysis Set and subjects will be classified according to their randomized treatment group. The primary endpoint analysis will also be performed on the PP set as a sensitivity analysis to the results on the FAS. The summary of additional endpoints will also be performed on the Full Analysis Set. Analysis of the primary safety endpoint and adverse event summaries will be performed on the Safety Set.

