# 9.2 REPORTING PROCEDURES FOR ADVERSE EVENTS/PRODUCT COMPLAINTS

#### 9.2.1 Reporting Adverse Events

Data related to AEs will be recorded in the source documentation from the time of study enrollment (first incision) until the subject completes the study or terminates early. All AEs that are unresolved at study completion (or early termination) will be recorded as ongoing at study end.

Data related to SAEs will be collected until event resolution, or until the event is considered stable, or until all attempts to determine the resolution of the event are exhausted.

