Additional summaries will be provided to tabulate the total number of vessels transected as well as the specific type of vessel that was transected – renal artery or renal vein. The specific types of interventions that were performed will also be tabulated by randomized treatment group.

The primary safety endpoint, the occurrence of hemostatic interventions/procedures completed for post-operative bleeding related to the transection of the RA and RV, is measured at the subject level and will be analyzed using the same methodology as described above for independent observations. A similar dataset will be created that contains one record per subject and an indicator for whether or not the subject experienced a post-operative intervention event. The SAS code provided above will be utilized in a similar manner for this analysis.

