Two-sided 95% Confidence Interval for Percent Difference (One-sided 95% CI Upper Limit) for Percent Requiring Transection [2]	xx.x%, xx.x%	xx.x%, xx.x%	xx.x%, xx.x%
	xx.x% (xx.x%)		
Type of Intervention, n (%) [3]			
Additional Stapling	xx (xx.x%)	xx (xx.x%)	xx (xx.x%)
Over-sewing	xx (xx.x%)	xx (xx.x%)	xx (xx.x%)
Compression	xx (xx.x%)	xx (xx.x%)	xx (xx.x%)
Use of Suture	xx (xx.x%)	xx (xx.x%)	xx (xx.x%)
Sealant	xx (xx.x%)	xx (xx.x%)	xx (xx.x%)
Buttress	xx (xx.x%)	xx (xx.x%)	xx (xx.x%)
Use of Energy	xx (xx.x%)	xx (xx.x%)	xx (xx.x%)
Clip Placement	xx (xx.x%)	xx (xx.x%)	xx (xx.x%)
Blood Product Transfusion	xx (xx.x%)	xx (xx.x%)	xx (xx.x%)
Additional Surgical Procedure	xx (xx.x%)	xx (xx.x%)	xx (xx.x%)
Other Intervention	xx (xx.x%)	xx (xx.x%)	xx (xx.x%)
Intervention Category, n (%) [4]			
No Intervention	xx (xx.x%)	xx (xx.x%)	xx (xx.x%)
Hemostasis Controllable	xx (xx.x%)	xx (xx.x%)	xx (xx.x%)
Hemostasis Intervention	xx (xx.x%)	xx (xx.x%)	xx (xx.x%)

[1] Denominator for calculation of percentage is the total number of vessels transected in that group.

[2] Difference is calculated as Powered Vascular Stapler minus Standard of Care Stapler.

[3] Denominator for calculation of percentage is the total number of vessels requiring intervention in that group.

[4] Hemostasis Controllable includes additional stapling, over-sewing, compression, use of suture, sealant, buttress, use of energy, clip placement, or other intervention.
 Hemostasis Intervention includes blood product transfusion and additional surgical procedure.

Table 7
 Post-Operative Interventions or Procedures Related to Renal Artery or Renal Vein Bleeding
 Safety Set

Characteristics	Standard of Care Stapler (N = ##)	Powered Vascular Stapler (N = ##)	Overall (N = ##)
Number of Subjects Requiring Post-Operative Intervention Related to Renal Artery or Renal Vein Bleeding			
n (%) [1]	xx (xx.x%)	xx (xx.x%)	xx (xx.x%)
95% Confidence Interval for Percent	xx.x%, xx.x%	xx.x%, xx.x%	xx.x%, xx.x%
Type of Intervention, n (%) [2]			
Blood Product Transfusion	xx (xx.x%)	xx (xx.x%)	xx (xx.x%)
Additional Surgical Procedure	xx (xx.x%)	xx (xx.x%)	xx (xx.x%)
Other Intervention	xx (xx.x%)	xx (xx.x%)	xx (xx.x%)

[1] Denominator for calculation of percentage is the total number of subjects in that group.
 [2] Denominator for calculation of percentage is the total number of subjects requiring intervention in that group.

Table 8
 Device Usage Details
 Full Analysis Set

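### Protocol 4.4 forces withdrawal during surgery without securing post-operative follow-up, while SAP Table 7 keeps those subjects in the primary safety denominator

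*Protocol*

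**What the plan says.** **Withdrawal.** Protocol 4.4, under Surgical, makes withdrawal mandatory: "The Investigator must withdraw a subject intraoperative for the following reasons". Three reasons follow:

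- "A simple or radical laparoscopic nephrectomy or laparoscopic nephroureterectomy not completed". No follow-up is stated.
- "Conversion to an open procedure, unless directly related to transection of the RA/RV (subject will be followed for safety up to 30 days postop"). This is the only follow-up wording in the list.
- "Use of robotic assistance during surgery". No follow-up is stated.

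The opening of 4.4 promises an effort to obtain final-visit data, but for a subject (or representative) who decides to withdraw. It does not mention withdrawal imposed by the investigator. Protocol 9.2.1 has adverse events recorded "until the subject completes the study or terminates early", and follows serious adverse events until they resolve or stabilise.

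**Endpoint collection.** Post-operative interventions for renal artery or vein bleeding are collected at Visit 3 (Protocol 4.7.4) and Visit 4 (Protocol 4.7.5). SAP section 4 confirms this.

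**Analysis.** Protocol 7.3 states: "The Safety Set consists of all randomized subjects on whom the procedure is started". SAP section 7 agrees and assigns the primary safety endpoint to that set. SAP 10.4 builds a dataset with "one record per subject and an indicator for whether or not the subject experienced a post-operative intervention event". Footnote 1 of Table 7 reads: "Denominator for calculation of percentage is the total number of subjects in that group". SAP 10.6 and Protocol 7.5.1 restrict summaries to observed data and rule out imputation, including for subjects who terminate early.

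**The concern.** None of the three withdrawal reasons is limited to subjects whose vessels have not yet been stapled. A subject can have the renal artery and vein transected with the assigned device, then be converted, left incomplete or finished robotically, and be withdrawn on the table. That subject has been exposed to the device and is at risk of post-operative bleeding, but the protocol does not clearly require anyone to ask about it.

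The subject is still in the Safety Set. With no post-operative data, he or she adds one to the Table 7 denominator and cannot add to the numerator. The reported bleeding rate then falls for the operations that did not go to plan, in the direction that favours the primary objective, which covers post-operative as well as intra-operative interventions. The study is open-label, and whether a conversion is attributed to the vessel transection is judged with the device known. Losses could therefore differ between arms, although nothing in the documents shows that they would.

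**Working it through.** **1. Does each withdrawal reason carry a duty to collect the endpoint?**

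| Reason in Protocol 4.4 | Follow-up in the bullet | Final-visit effort in 4.4 | AE recording in 9.2.1 |
|---|---|---|---|
| Not completed | None | Worded for subjects who decide to withdraw | Ends at early termination |
| Non-vascular conversion to open | 30 days for safety, scope unclear | Same | Same |
| Robotic assistance | None | Same | Same |

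The conversion parenthesis can be read in two ways. It may cover the withdrawn conversions, or only the excepted subjects whose conversion was due to the vessel transection. The excepted subjects stay in the study and have Visits 3 and 4 anyway, which favours the first reading. On that reading, however, the bullet disagrees with 9.2.1, which stops adverse event recording at early termination. Neither reading says that the primary safety endpoint itself is collected.

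**2. How would an unobserved subject be counted?** Table 1 of the SAP lists Surgical as a discontinuation reason with percentages on the Safety Set, so these subjects are in that set. SAP 10.4 needs an indicator for each of them but gives no rule for unknown status. Footnote 1 of Table 7 divides by everyone. SAP 10.6 says to summarise only what was observed. The last two cannot both be followed.

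**3. Size.** The plan's only precision figure is the 2.9% margin for the intra-operative rate (6%, 300 firings). It reproduces: the Clopper-Pearson interval for 18/300 is 3.59% to 9.32%, a half-width of 2.86%; the Wald half-width is 1.96 × √(0.06 × 0.94/300) = 2.69%. No figure is given for the safety endpoint, and this one does not enter below.

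Inputs: about 250 subjects at 1:1 gives 125 per arm (Protocol 7.2), with exact two-sided 95% limits (SAP 10.4). The unobserved share and the event counts are assumptions, because the documents give neither. Let x be the observed events and m the unobserved subjects per arm.

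- Table 7 as footnoted: x/125.
- Observed only: x/(125 − m).
- Their ratio: (125 − m)/125.
- All unobserved had an event: (x + m)/125.
- Upper limit with x = 0: 1 − 0.025^(1/n). For n = 125 this is 2.91%.

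| Assumed share unobserved (m) | Followed | Upper limit, x = 0, followed only | Rate, x = 2, n = 125 | Rate, x = 2, followed only | x = 2, all unobserved counted as events |
|---|---|---|---|---|---|
| 2% (2) | 123 | 2.95% | 1.60% | 1.63% | 3.2% |
| 5% (6) | 119 | 3.05% | 1.60% | 1.68% | 6.4% |
| 10% (12) | 113 | 3.21% | 1.60% | 1.77% | 11.2% |
| 15% (19) | 106 | 3.42% | 1.60% | 1.89% | 16.8% |

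At 5-10% unobserved and no events, the denominator alone moves the upper limit by 3.05 − 2.91 = 0.14 to 3.21 − 2.91 = 0.30 percentage points. Missed events matter more: two among the unobserved would turn 0/125 into 2/125 = 1.6%, with an upper limit of 5.66%.

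**The case against.** A reader might infer that withdrawn subjects skip Visits 3 and 4, and that Table 7 declares them event-free. The documents say neither. No section exempts them from post-operative collection, and the conversion bullet contains a 30-day safety follow-up that would span discharge and the 4-week visit. Scoring an unobserved subject as no event would be imputation, which SAP 10.6 forbids. It is the arithmetic effect of one table-shell footnote, not a stated rule.

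Other points limit the problem:

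- SAP section 3 says sites were told to randomize as close as possible to vessel transection. Many conversions or robotic changes would then precede randomization. Some subjects withdrawn later may never have been stapled and would not be at risk.
- Table 1 will show surgical discontinuations and losses to follow-up by arm, and the listings cover post-operative interventions, withdrawal and visits.
- A subject lost to follow-up may still have Visit 3 data, so is partly observed and not equivalent to one withdrawn in the operating room.
- The 3% acceptance criterion applies to the intra-operative difference per firing. No criterion depends on the safety endpoint.

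All of this stands, and it bounds the number affected and the consequence. It does not supply the missing follow-up requirement for non-completion and robotic use, settle the scope of the conversion wording, or remove the conflict between footnote 1 and SAP 10.6. Table 1 counts discontinuations, not subjects whose post-operative bleeding status is unknown. Following serious events to resolution does not clearly oblige anyone to look for new ones after termination.

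**Conclusion.** The point holds as a gap and a conflict between sections, of moderate severity. For two of the three mandatory withdrawal reasons no post-operative follow-up is stated, and for the third its scope is ambiguous. A subject already exposed to the stapler may have no required collection of the primary safety endpoint and still be counted in its denominator.

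The denominator effect is small: 0.14 to 0.30 percentage points on the upper limit under an assumed 5-10% unobserved, 125 per arm and no observed events. The larger uncertainty is events never ascertained, which Table 7 as laid out would not reveal. The documents do not support a claim that the safety result is materially wrong, that losses differ by arm, or that a pass/fail decision would change.

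**What to change.** 1. **Protocol 4.4 and 9.2.1.** Reconcile the opening of 4.4, the Surgical list and the end of adverse event recording. State that surgical withdrawal does not end Visit 3 and Visit 4 collection of post-operative interventions and adverse events for any randomized subject whose procedure was started, unless consent is withdrawn. Say which subjects the 30-day wording covers.
2. **SAP 10.4, 10.6 and Table 7.** Use Safety Set subjects with observed post-operative status as the denominator, show the number unobserved per arm, and add one sensitivity line counting the unobserved as events. State how partly observed subjects (Visit 3 only) are classed.

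The cost is some protocol wording, a footnote and two table rows, a few extra contacts per site (Visit 4 may already be a telephone call), and a slightly wider interval. The SAP describes study conduct in the past tense, so the protocol change may come too late to alter collection. The SAP change needs no new data and can be made before database lock.
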